IMPLEMENTATION OF THE INTERVENTION

SUMMARY

The project is now ready to move into the intervention, informed by the formative research phase, aligned with Objective #3. The intervention targets households with moderately malnourished children between 7 and 15 months of age, and will follow and support these households for a period of 6-months. Consent will be obtained from mothers via thumbprint or signature. Severely malnourished children, regardless of group, will be referred to local health facilities for care. Households in the control group will continue with their usual feeding and care practices.

This study is rooted in an asset-based approach grounded in the belief that in every community there are certain individuals whose uncommon behaviours enable them to find solutions to prevalent and seemingly intractable problems. The intent of the formative research phase supported by the CAC was to learn what is already possible within the community of Rahim Yar Khan and to amplify these strategies to the wider community during the intervention phase. The intervention comprises of two major components: community sensitization and a 28-day behaviour change period.

COMMUNITY SENSITIZATION OVERVIEW

The community sensitization events will be held in each intervention cluster. These events will introduce the project to local families about complementary feeding for children 6-23 months of age. These sessions will be delivered using town-hall format with small group activities. Key messages supported with visuals and print materials from the 28-day behavior change program (discussed below) will be shared with the larger community. The objective of the community sensitization programs is to create community awareness about the project, share best practices related to complementary feeding with the wider community with the hope this will promote community buy-in as well as community and neighborhood support for households participating in the 28-day change program.

28-DAY BEHAVIOR CHANGE PRACTICE PROGRAM OVERVIEW

Prior to recruitment and starting the 28-day behavior change program, each child will undergo a health check by a physician at the local health facility, including anemia screening, and ensuring they are up to date with all required immunizations.

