4. ELIGIBILITY ASSESSMENT

To determine eligibility for participation, each Index Child will undergo a multi-step assessment process.

- Assessment of the child's nutritional status. Only those children identified as being moderately malnourished admitted into the study. Children will be assessed by the field staff through anthropometric measurements: weight, length/height, and mid-upper arm circumference (MUAC) and using standardized WHO growth reference tools. Children will only be included if they are classified as moderately underweight (weight-for-age Z-score between -2 and -3 SD). Severely malnourished children will be referred immediately to a health facility for medical care. All measurements will be conducted by trained staff following strict protocols to ensure consistency and accuracy.

To be eligible for the Treatment Arm. All children meeting the classification of moderate malnutrition will undergo a complete medical at the local health facility, including confirmation of their nutritional status and update of their vaccination record. Eligibility will be determined by working with the Lady Health Worker affiliated with the respective household, who will rule out children with chronic disease according to the exclusion list. A final confirmation from the health facility will be sought after consent is obtained to assess whether the child is well enough to participate in the 28-day behavior change (Hearth) program.

- To be eligible for the Control Arm. All children meeting the classification of moderate malnutrition will be assessed for chronic illness. Initial assessment will be done by asking mothers about their child's health and final eligibility confirmed by Lady Health Workers' medical records.
- Assessment of the household eligibility. Households will undergo an assessment of their wealth ranking and food security status. Study staff will use the Final Recruitment Screening Form to confirm and document eligibility for participation. The recruitment forms for both the treatment and control arms are attached in Section 9.5.

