5. CONSENT PROCESS

If the above eligibility criteria are met, on the same day, study staff will discuss the details of the consent process with the household and prepare for the signing of the consent document. The households in the treatment arm will then visit the health facility within one week for medical clearance. One week later, staff will visit the household to collect the signed consent form and conduct the baseline survey. Clearance from the health facility must be obtained before the household begins Hearth sessions. This clearance serves as a second check for exclusion due to disabilities or chronic disease.

To ensure that every participant fully understands the nature of the study before deciding to take part, the informed consent process will be conducted with care, cultural sensitivity, and attention to literacy needs. All consent materials will be provided in Punjabi and Saraiki, the local languages most commonly spoken in the study communities. Trained field staff will visit households in person to explain the study using simple, conversational language. They will walk families through all key aspects of participation, including the purpose and title of the research, the expected duration and structure of the study, what will be asked of them, and what potential risks or benefits may arise.

As this is a community-based study intended to test the feasibility of this intervention in rural Pakistan, the consent process will carefully explain the purpose, procedures, and expectations. This will include what health assessments will be conducted, how data will be collected and stored, and the confidentiality protections in place. Importantly, participants will be reminded that their involvement is entirely voluntary, and they may withdraw at any time without penalty or consequence, as outlined clearly in the consent form. While the study will obtain written

consent at the time of recruitment, on-going verbal consent will be sought at critical junctures to reaffirm willingness to participate. For example, for the Treatment Arm, this will include prior to engaging with hearth cycles 2 and 3 if participants are eligible, and prior to conducting follow-up surveys at 6 and 12 months. At households' request, trusted community members may also be engaged to help explain the protocol and answer questions. Each participating household will receive a printed copy of the consent form for their own records.

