Anthropometric Assessment. Each Index Child's weight and height will be measured at the start and end of each hearth session, and at the end of the 2-week home visits (Day 1, Day 13, Day 27 of each cycle). If, by the end of the cycle, the child has not gained at least 400g, they will be invited to repeat the cycle—up to a maximum of three cycles. Children failing to any gain weight between cycles will be referred to a public health facility for medical evaluation. Z-Scores will be calculated to quantify the child's nutritional status. Mid-Upper Arm Circumference (MUAC) will be taken to assess for wasting. During the follow-up period, the child's weight will be monitored monthly for up to six months post-intervention.

Health assessment.

Baseline health assessments will be conducted at local public health facilities within two weeks prior to the first Hearth session for participants in the treatment arm. Each Index Child will receive a full medical examination by a physician, a Hematocrit (Hb) test via finger prick, and verification and updates for routine immunizations.

All children showing "failure to thrive" (e.g., no weight gain or weight loss after a Hearth cycle) will be referred for medical assessment within five days, and accompanied by study staff.

Results of participants' health assessments will not be shared or retained by the research team. This assessment will be conducted solely to confirm that the child meets eligibility criteria and is well enough to participate in the 28-day behaviour change program. This information is sufficient for enrollment purposes, and no medical or health records beyond the anthropometric measurements will be collected, stored, or used as study data

Data collection

Data will be collected using structured tools and include:

Baseline and follow-up household surveys (at 6 months, and possibly 12 months post-intervention if funding permits): surveys will assess 24-hour food recall and indicators on feeding practices, WASH, gender roles, and health-seeking behaviour. Study survey instrument is attached to Section 9.5.

All data will first be recorded on paper and later digitized by trained personnel.

PROCEDURES FOR PARTICIPANTS IN THE CONTROL ARM

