- consent signing 0.5 hours,
- baseline survey 1.25 hours,
- final 6-month survey 1 hour,

- anthropometric measurement 1.5 hours (0.25 hours x 6, includes measurement taken at baseline, follow-up, and final assessment).

Obtaining Consent

On the day of final recruitment, details of the study and the consent process will be explained to mothers. Households will then have one week to reflect on the information provided. During a home visit one week later, and just before the baseline survey, trained staff will obtain informed consent from the mother of the index child. The staff has gone through training to ensure they communicate the following in lay-person language, and in a clear and respectful manner: research time-frame; title of research; researchers involved; purpose of research; description of research; potential harms and benefits; treatment alternatives; statement of confidentiality; information and data to be collected; how long the data will be kept, how it will be stored and who can access it; any conflicts of interest; a statement of the participant's right to withdraw from participation at any point; and a declarative statement of understanding that the potential participant agrees to and signs.

- A copy of the consent form will be provided to the parents of Index child.
- Parents will authorize by signing the consent form that they have read and understand this consent form, and volunteer to participate in this research study.
- For eligible participants with limited literacy, parents will authorize using thumbprint signature that they understand the consent form and volunteer to participate in this research study.

Informed Consent from the Treatment Arm households will be obtained 1 week after communicating the study information with the participants, and 1-2 weeks prior to the 28-Day Behavior Change Practice sessions, and before participants participate in the baseline survey.

Informed Consent from the Control Arm households will be obtained 1 week after communicating the study information with the participant, and before participants in the baseline survey.

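### The protocol gives no single order for signed consent and the treatment-arm facility check; in two places the order puts an examination and finger-prick of the infant before the mother has signed

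*Protocol*

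**What the plan says.** The Protocol places the treatment-arm facility check relative to consent in several sections:

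- **28-Day Behavior Change Practice Program Overview:** here the check comes first. "Prior to recruitment and starting the 28-day behavior change program, each child will undergo a health check by a physician". The same sentence includes anemia screening.
- **Recruitment Methods, 4. Eligibility Assessment:** for the treatment arm, "All children meeting the classification of moderate malnutrition will undergo a complete medical at the local health facility", listed as an eligibility step. Shortly afterwards: "A final confirmation from the health facility will be sought after consent is obtained".
- **Recruitment Methods, 5. Consent Process:** once eligibility is met, staff discuss the consent details that same day. "The households in the treatment arm will then visit the health facility within one week for medical clearance". Then: "One week later, staff will visit the household to collect the signed consent form and conduct the baseline survey". Clearance is required before Hearth begins and is described as a further check for exclusion.
- **Obtaining Consent:** "During a home visit one week later, and just before the baseline survey, trained staff will obtain informed consent from the mother". For the treatment arm, consent is placed 1 to 2 weeks before the 28-day program.
- **Procedures, Health assessment:** the check takes place within two weeks before the first Hearth session. "Each Index Child will receive a full medical examination by a physician, a Hematocrit (Hb) test via finger prick". Its only stated purpose is to confirm eligibility and fitness for the program.
- **Mother Eligibility Criteria:** the mother's agreement to the check-up and the one-time finger-prick is item 8; informed consent is a separate item 9.
- **Procedures for the control arm:** controls have no facility assessment at baseline.

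**The concern.** The finger-prick is described as a single test, so it cannot fall both before and after signed consent. The examination is done for the study rather than as routine care: its stated purpose is eligibility and fitness for Hearth, and control children, who keep routine care, do not have it. Field staff who follow the overview or the Consent Process section would have an infant examined and finger-pricked before the mother has signed. Staff who follow the sentence on final confirmation would wait for consent. What is at stake is first the protection of participants, and second whether a treatment-arm child who fails clearance drops out before or after consent.

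**Working it through.** There is no sample-size, power or error-rate figure to reproduce. The check is a comparison of sections plus a day count.

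**1. Position of the check relative to consent**

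| Section | Facility check | Signed consent |
|---|---|---|
| Program overview | before recruitment | not stated there; elsewhere at or after recruitment |
| Eligibility Assessment, complete medical | eligibility step | consent discussion follows eligibility |
| Eligibility Assessment, final confirmation | after consent | before the confirmation |
| Consent Process | within one week of the discussion | form collected after that visit |
| Obtaining Consent | not stated | home visit one week after the information is given |

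The Consent Process section elsewhere ties written consent to the time of recruitment, while Obtaining Consent has the study explained on the day of final recruitment and consent taken a week later. On either account, a check done ahead of recruitment is ahead of consent.

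**2. Day count under Consent Process and Obtaining Consent**

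Inputs: discussion = day 0; facility visit on days 0 to 7; consent about day 7; Hearth 7 to 14 days after consent.

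- Hearth starts between day 7 + 7 = 14 and day 7 + 14 = 21.
- Check to consent: between 7 − 7 = 0 and 7 − 0 = 7 days, with the check first.
- Check to Hearth: shortest 14 − 7 = 7 days, longest 21 − 0 = 21 days.
- Window in Health assessment: at most 14 days. An interval of 7 to 21 days can exceed it.

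If the week in the Consent Process section is counted from the facility visit instead, consent is 7 days after the check. Hearth is then 7 + 7 = 14 to 7 + 14 = 21 days after the check, which meets the window only at exactly 14 days.

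**3. Day count with consent first**

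The check falls between consent and Hearth. Hearth is 7 to 14 days after consent, so the check is 0 to 14 days before Hearth and always meets the window.

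**4. How many children**

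The planned treatment arm is 100 households, or 100 × 1.2 = 120 if the 20% attrition buffer is added on top. This is an upper limit on how many enrolled children could be affected, not an estimate.

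**The case against.** **Two facility contacts.** The Eligibility Assessment section may describe a medical first and a confirmation later, and the Consent Process section could fit that: visit, form collected, clearance in hand before Hearth. This softens the conflict between those two sections. It does not remove the problem, because the medical itself would still come before signed consent.

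**The form may have been signed earlier in the week.** Collecting a signed form does not by itself say when it was signed. But Obtaining Consent says that consent is obtained at that visit, just before the baseline survey.

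**The mother is informed and has agreed.** Under the Consent Process section the study is discussed before the facility visit, and item 8 of the maternal criteria requires agreement to the check-up. The check's results are not kept as study data. The consent and screening forms are not shown, so a separate screening permission cannot be ruled out. This context stands and lessens the gravity. It does not stand in for signed consent, which the protocol lists as its own item.

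**The finger-prick is inferred.** The Eligibility Assessment and Consent Process sections do not name it. The link comes from the overview's anemia screening, item 8 and the Health assessment section. This is a fair limit on the reading, but no other facility check at baseline is described.

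**A stronger reading that does not hold.** A reader might infer that the order biases the comparison toward treatment. If a fraction f of treatment-arm children is removed and none of them would have reached the endpoint, the proportion p rises to p/(1 − f). That expression has no term for order: it gives the same value for removal before consent and after it. What it describes is screening in one arm only, which re-ordering does not cure. The protocol gives no value for f, clearance is a second check after the Lady Health Worker's, and whether children who fail would have missed the endpoint is unknown. Nor does the protocol support requiring that such children stay in the analysis set; that choice is debatable and may belong to the SAP.

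**Conclusion.** The point holds as an internal inconsistency with a consequence for participants. The sections on the overview, eligibility, consent and health assessment do not yield one order. Two of them, read with Obtaining Consent, put a study-only examination with a one-time finger-prick before the mother's signature, though under the Consent Process section after a verbal discussion. At worst it affects all treatment-arm children. The same order gives a check-to-Hearth interval of 7 to 21 days against a stated limit of two weeks, while consent first gives 0 to 14 days.

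This rests on two readings: that there is one baseline facility check containing the finger-prick, and that consent is given when Obtaining Consent says it is. No percentage-point effect on the primary comparison is claimed.

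**What to change.** Reconcile the overview, Eligibility Assessment, Consent Process, Health assessment and Obtaining Consent sections to one order:

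1. information visit;
2. signed consent and baseline survey about one week later;
3. facility check;
4. Hearth Day 1.

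In the overview, delete the opening phrase that places the check ahead of recruitment. In Eligibility Assessment, make clear whether the complete medical and the final confirmation are the same contact, and place the examination after signed consent. The requirement for clearance before Hearth stays as it is.

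In this order clearance becomes a treatment-arm-only exclusion that falls after consent, so record the number of consented children who fail it. A count does not require the team to keep any medical result, so it fits the Health assessment section's statement that results are not retained.

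The cost is wording and visit sequence. Obtaining Consent already leaves 1 to 2 weeks between consent and Hearth for the check. The one practical loss is a baseline survey (1.25 hours in the protocol's time estimate) for each household whose child then fails clearance.

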Participants in the control group will be enrolled after staff use the Final Recruitment Screening for Control Form to confirm eligibility, and households that express interest will be invited to join. Unlike the intervention group, control participants will not undergo a health facility-based assessment at baseline, will also not participate in the 28-day behavior change practice program, and will instead continue to receive routine care from LHWs and access health services as usual.

They will participate in the baseline and follow-up household surveys (at 6 months, and possibly 12 months post-intervention if funding permits): surveys will assess 24-hour food recall and indicators on feeding practices, WASH, gender roles, and health-seeking behaviour. Study survey instrument is attached to Section 9.5.

Anthropometric Assessment. Each Index Child's weight and height will be measured at the time of baseline and endline survey. Z-Scores will be calculated to quantify the child's nutritional status. Mid-Upper Arm Circumference (MUAC) will be taken to assess for wasting. During the follow-up period, the child's weight will be monitored monthly for up to six months post-baseline.

Time to Participate

For Treatment arm:

If a household were to partake in one hearth cycle and complete the full 6-month participation we will be offering, we can estimate the total time participants would need to commit is 40 hours over a 6-month period.

- initial recruitment assessment 0.5 hours,
- consent signing 0.5 hours,
- baseline survey 1.25 hours,
- final 6-month survey 1 hour,
- anthropometric measurement 1.5 hours (0.25 hours x 6, includes measurement taken at baseline, follow-up, and final assessment).
- 28-Day Behavior Change Practice Program. Hearth Sessions Total 34.5 hours: 12 days per cycle, 2.5 hours per day, for total = 30 hrs. Home-visits during the second half of the program total of 4.5 hours (1.5 hours three time a week for two weeks),
- Health Assessment at the medical facility may take up to 1 hour for medical screening, immunization checks, and collection of baseline height and weight measurements.

If the household participates in three hearth cycles, the time the staff will spend at the family's home is estimated to be 74.5 hours.

For Control arm:

If a household were to complete the full 6-month participation, we can estimate the total time participants would need to commit is 4.75 hours.

- initial recruitment assessment 0.5 hours,

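### One child exclusion list, but a physician clearance that can exclude only in the treatment arm: growth-slowing illness missed at first screening can be removed from one side of the comparison (size unknown, probably small)

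*Protocol*

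**What the plan says.** The Exclusion Criteria section has one child-level list, not split by arm. It covers disabilities and chronic illnesses that could impair growth, the latter judged from past or present medical history.

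The list is applied differently in the two arms:

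- **Controls** (Recruitment Methods, 4. Eligibility Assessment): "Initial assessment will be done by asking mothers about their child's health and final eligibility confirmed by Lady Health Workers' medical records". The control-arm procedures add that "control participants will not undergo a health facility-based assessment at baseline".
- **Treatment, first stage** (same section): the text relies on the LHW, "who will rule out children with chronic disease according to the exclusion list". It also requires a medical at the facility, "including confirmation of their nutritional status and update of their vaccination record".
- **Treatment, second stage** (5. Consent Process): clearance is needed before Hearth starts, and "This clearance serves as a second check for exclusion due to disabilities or chronic disease".

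Procedures, Health assessment, describes the physician examination as an enrolment step: "This assessment will be conducted solely to confirm that the child meets eligibility criteria and is well enough to participate", and "This information is sufficient for enrollment purposes". It also says that results of "health assessments will not be shared or retained by the research team".

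The Study Hypothesis compares the arms on the proportion of children averaging 400 g per month over the first four months.

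**The concern.** The extra filter acts on a cause of the outcome, and in one arm only. For chronic illness that the first screen missed, one-sided removal makes the treatment arm healthier and so probably favours the intervention.

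Two smaller asymmetries sit beside it. The control screening text names chronic illness but not disability, whereas the treatment clearance names both. The treatment medical also re-confirms nutritional status, so the weight criterion is checked again in one arm only.

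The point belongs in the protocol because field procedure decides who is weighed. The protocol does not say whether a treatment child who is not cleared stays in follow-up. If such children are not weighed, and the examination results are not kept, no later analysis can bring them back. The survey's item on child health status would allow only partial adjustment.

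**Working it through.** **The plan's own figure.** 2. Sample Size gives 100 households per arm, 80% power and a difference of at least 400 g, without alpha, SD or responder rates, so it cannot be reproduced. Inverting the two-sample formula at two-sided 5% gives an implied SD of 400 / ((1.960 + 0.842) × √(2/100)) ≈ 1,010 g. The point here does not depend on it; only n = 100 per arm is used below.

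**Bias from one-sided removal.** Every rate here is assumed, since the protocol gives none. Let f be the share of children the second check would remove, p the response rate of cleared children and q that of uncleared children. With no true effect:

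- treatment rate = p
- control rate = (1 − f)p + fq
- spurious difference = f(p − q), at most fp

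The false-positive rate is that of a pooled two-proportion z test, two-sided 5%, n = 100 per arm, independent children.

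Example: p = 20%, f = 10%, q = 0. The control rate is 18% and the difference 2.0 points. The null SE is √(2 × 0.19 × 0.81/100) = 0.0555, and the SE under the two rates is also 0.0555. Rejection = Φ(−1.60) + Φ(−2.32) = 0.055 + 0.010 = 6.5%.

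| p | q | f = 5%: bias, false positives | f = 10%: bias, false positives |
|---|---|---|---|
| 10% | 0 | 0.5 points, 5.2% | 1.0 points, 5.7% |
| 20% | 0 | 1.0 points, 5.4% | 2.0 points, 6.5% |
| 20% | 10% | 0.5 points, 5.1% | 1.0 points, 5.4% |
| 50% | 0 | 2.5 points, 6.4% | 5.0 points, 10.9% |

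At f = 2% the false-positive rate is at most 5.2%, even with p = 50%. For scale, 100 per arm detects 15.0 points at a base rate of 10% and 17.9 points at 20% (80% power).

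**The weight recheck.** This was simulated with assumed inputs: weight-for-age Z mean −1.5 and SD 1.1; 1 Z = 0.9 kg; four-month gain SD 0.4-0.6 kg; base rate 10-20%; weighing error SD 0.1-0.2 kg. Treatment children must fall between −3 and −2 twice, controls once. The effect on the treatment response rate depends on the starting weight used:

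- gain counted from the recruitment weight: about 0.1 to 1.2 points lower
- gain counted from a fresh baseline-survey weight: about 0
- gain counted from the facility weight in treatment and the survey weight in controls: about 0.1 to under 1 point higher

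The third case is possible because Time to Participate lists baseline height and weight among the facility procedures. Under the same inputs about 12% (error 0.1 kg) to 25% (0.2 kg) of treatment children fail the recheck.

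**Dilution if uncleared children are included.** Assume they gain nothing from the programme, so the difference becomes d(1 − f). At base 20% and 100 per arm:

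- f = 5%: 17.9 × 0.95 = 17.0 points, power about 76%
- f = 10%: 17.9 × 0.90 = 16.1 points, power about 72%
- recheck failures also counted as uncleared (12% or 25%): power about 70% or 58%

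**The case against.** **The effect is too small to matter.** At plausible base rates it is a fraction of the detectable difference, and the 10.9% false-positive rate needs three unfavourable assumptions together. The list also defines chronic illness by medical history, which mother report and LHW records address, so few children may be missed. This stands, and it limits the point to a modest one.

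**The protocol does not say that uncleared children are dropped.** The anthropometry section schedules recruitment, baseline, monthly and endline measurement for treatment and control children without making it conditional on clearance. This stands too. A reader might infer that these children are certainly lost, but the text is silent rather than explicit. The loss is a risk that one sentence would remove.

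**A reader might infer a known bias towards the intervention.** The documents do not support that. The weight recheck can act in either direction, a temporarily unwell child may rebound, and the mother interview is described for controls only, so controls may lose some children that the LHW step misses.

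**Controls are not screened merely once.** Their screen has two steps. Both are non-clinical, however, and no physician can exclude a control child. The screening forms, which the protocol places in its Section 9.5, are not in the text at hand and may narrow the first-stage difference; they cannot supply the missing examination.

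**Keeping physician-excluded children in the primary set conflicts with the exclusion list.** This is a fair trade-off to debate. The fix therefore asks for both analyses and leaves the choice of primary set to the SAP.

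**The arms are non-randomised Union Councils anyway.** True. This difference, unlike those between areas, is created by procedure and can be bounded by procedure.

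**Conclusion.** The asymmetry is stated in the protocol: a physician clearance that can exclude exists in the treatment arm and is ruled out for controls, under one exclusion list tied to growth. Its size is unknown. With 5-10% removed, no response among those removed and base rates of 10-20%, it is about 0.5-2.0 points, with a false-positive rate of 5.2-6.5%. With half the response among those removed, it is 0.25-1.0 points. The net direction is not certain, and it adds to an already non-randomised comparison. These figures assume independent children and 100 analysed per arm; clustering by Union Council is not modelled.

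It is worth fixing because without a count of uncleared children the sponsor could not later show that the effect was small.

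**What to change.** 1. In 4. Eligibility Assessment, use the same first-stage screen in both arms: mother report plus LHW records, against the full child exclusion list including disabilities.
2. In 5. Consent Process and Health assessment, leave facility clearance, its role for Hearth attendance and any referral unchanged. Record cleared yes/no and one broad reason (exclusion list, nutritional status, not well enough), with counts and no medical results. Staff already need the yes/no before Hearth starts.
3. State that treatment-arm children who passed the common screen and whose mothers consented, but who were not cleared, are offered the baseline, monthly and endline weighing already scheduled.
4. Report the between-arm comparison with and without these children. Which set is primary may be left to the SAP.
5. Reconcile the programme overview (health check before recruitment), 4. Eligibility Assessment (a medical under eligibility, then a confirmation after consent), 5. Consent Process (a sequence that can be read two ways) and Obtaining Consent on whether clearance precedes signed consent. Step 3 depends on this.

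**Cost.** Some protocol and form wording, plus family time. From the control-arm budget this is 4.75 − 0.5 (screening already done) = 4.25 h per uncleared child: about 21-43 h for 5-10 families, or 51-106 h for 12-25 families if recheck failures count. The analysis that includes these children has the diluted power shown above. If the 20% buffer means 120 per arm and nobody is lost, power is about 83% at 5% uncleared and 79-80% at 10%.

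The alternative, the same facility check for controls, removes the asymmetry at source. It needs about 100 or more extra facility visits, however, and gives controls part of what is now specific to treatment, against the routine-care control described in the procedures.
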